6.2 Allocation

After initial eligibility based on screening of the clinical data and kidney biopsy report, each patient will receive an explanation of the trial plan. After the signature of the consensus participation the patient will be enrolled and randomized separately in each trial (allocation 1 to 1 ratio) via a web-based program generating random numbers to ensure allocation concealment. Stratified randomization will be done by age and sex in renal centers. The follow-up study to measure the outcomes will consist of regular visits at the prescribed times to collect clinical and laboratory data and information on drug adherence. Before the trial is complete, each patient will receive a final outpatient visit.

6.3 Blinding

Allocation concealment will not be blinded to the group of the assignment.

6.4 Statistical Methods

Quantitative variables will be summarized in the presence of normal distribution values as mean \pm SD or median, and interquartile ranges in the presence of non-normally distributed variables. The between-arms comparisons of continuous variables will be performed by independent t-test or Mann-Whitney U test, as appropriate. The between-arms difference of the primary end point (i.e. in the between-arms difference of delta 24h proteinuria from baseline to 6 months in the ACiGAN trial and the between-arms difference of delta 24h proteinuria from baseline to 12 months in the CHRONiGAN trial will be expressed as mean difference and 95% CI. Categorical variables will be presented as absolute and percentage frequency. Proportions will be compared using the Pearson's X^2 test or Fisher's test, as appropriate. The time to event analysis will be performed by the Kaplan-Meier curves by comparing the experimental and control group by the log rank test. Multivariate analysis will be based on Cox's regression proportional hazard method and used to assess the relative risk associated with possible baseline prognostic factors such as sex, age, serum creatinine, eGFR, hypertension, histological lesions and therapy.

The primary analysis will be conducted according to the intention-to-treat approach in all randomized patients, irrespective of adherence to the assigned treatment. A per protocol analysis will be also performed. A secondary analysis by linear mixed models (LMM) or generalized estimating equations (GEE) of repeated measurements of eGFR and proteinuria will be also performed. The choice between the two analyses will closely depend on the distribution type of the outcome variables in our study cohorts.

In these models, data will be expressed as regression coefficients, 95% CIs and P value. All analyses will be performed using SPSS for Windows, 17.0 (SPSS Inc., North Sydney, Australia) and STATA/IC 13.1 for Windows (College Station, Texas, US). A *P* value less than 0.05 will be considered statistically significant.

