6. SAMPLE SIZE AND STATISTICAL METHODS

ACIGAN. Data from the literature (22,23) have shown a difference in renal survival between corticosteroids and controls when the researchers assumed a difference of 50% in the primary end point (i.e. in the between-arms difference of delta 24 hour proteinuria from baseline to 6 months) as clinically relevant. Therefore, we assume that a mean delta proteinuria from baseline to 6 months in patients treated with RASBs alone (control arm) is 0.6 ± 1.0 g/24 hours (\pm SD) versus a mean delta proteinuria that is 1.2 ± 1.0 g/24 hours (\pm SD) from baseline to 6 months in patients treated with RASBs and corticosteroids (experimental arm). Based on these assumptions, we calculated a sample size of

132 patients (66 patients per group including a 10% dropout rate) for a power of 90%, a two-sided significance level of 0.05 and 3 years of recruitment. If the number of the enrolled patients will be insufficient, the recruitment period will be extended for two years.

CHRONiGaN. Data from the literature (29-31) have shown a difference of renal survival between SGLT2is and controls. There are no data in the literature exploring the difference of renal survival or proteinuria between SGLT2is and steroids. Here, the researchers assumed an opportunistic sample of 300 patients for this first comparative study (150 patients per group, including a 10% dropout rate).

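### The primary comparison of proteinuria change is left to an unadjusted t-test or Mann-Whitney test; a pre-named analysis adjusted for baseline and stratification factors would be more precise at no extra data cost

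*Protocol*

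**What the plan says.** Protocol section 6.4 gives one rule for comparing continuous variables between arms: "The between-arms comparisons of continuous variables will be performed by independent t-test or Mann-Whitney U test, as appropriate". The next sentence turns to the primary endpoint, defined for the first trial as "the between-arms difference of delta 24h proteinuria from baseline to 6 months in the ACiGAN trial" and in parallel form for CHRONiGaN, and states that it "will be expressed as mean difference and 95% CI". No covariate is attached to that comparison. In section 6.4, baseline factors are listed only for the Cox regression. Repeated measurements are modelled, but not as the primary analysis: "A secondary analysis by linear mixed models (LMM) or generalized estimating equations (GEE) of repeated measurements of eGFR and proteinuria will be also performed".

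Section 6.2 describes the randomisation: "Stratified randomization will be done by age and sex in renal centers". The Synopsis foresees over 30 sites.

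The sample size in section 6 assumes that the mean change "in patients treated with RASBs alone (control arm) is 0.6 ± 1.0 g/24 hours" "versus a mean delta proteinuria that is 1.2 ± 1.0 g/24 hours" in the experimental arm. With 90% power and two-sided 0.05 this leads to "132 patients (66 patients per group including a 10% dropout rate"). CHRONiGaN has 150 per arm with no stated effect or SD.

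**The concern.** Three features of the primary comparison are poorly fixed.

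- **Baseline is not used.** Daily proteinuria is an entry criterion, so a baseline value exists for everyone. Change from baseline is usually correlated with baseline, and an unadjusted test on change leaves that explained variation in the error term. Any chance imbalance in baseline then passes partly into the estimate.
- **The stratification factors are not used.** Stratifying balances age, sex and centre between arms. A test that ignores them takes no credit for the balance, so its standard error is somewhat too large to the extent that these factors predict the outcome.
- **Test and estimate may not match.** Two tests are offered and neither is assigned to the primary endpoint. The t-test belongs with a mean difference and its confidence interval. The Mann-Whitney test addresses a different quantity, so its p-value and the reported interval could point to different conclusions.

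At stake is precision in both trials and a clear link between the primary p-value and the primary estimate.

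**Working it through.** **1. Reproduce the plan's own size (ACiGaN).** Inputs from section 6: difference 1.2 − 0.6 = 0.6 g/24 h, SD of change 1.0, two-sided 0.05, power 90%, dropout 10%.

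n per arm = 2 × (1.960 + 1.282)² × 1.0² / 0.6² = 58.4, so 59 evaluable. Then 59 / 0.90 = 65.6, so 66 per arm and 132 in total. This matches the protocol exactly. An exact t calculation gives 60, then 67, per arm. The trial is thus sized for an unadjusted two-sample comparison of raw change.

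**2. Effect of adjusting for baseline.** Let r be the correlation between baseline and follow-up proteinuria, with equal variance s² at both times.

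- Variance of change: 2s²(1 − r)
- Residual variance after adjustment: s²(1 − r²)
- Ratio: (1 − r²) / [2(1 − r)] = (1 + r)/2

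The SD of change is held at the protocol's 1.0, so the adjusted residual SD is √[(1 + r)/2]. Power = Φ(0.6 / [SD × √(2/59)] − 1.960). The protocol gives no r, so it is an assumption shown over a range.

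| r (assumed) | Variance ratio | Residual SD | Power, 59 per arm (normal) | Power (t) | Per arm for 90%, incl. 10% dropout |
|---|---|---|---|---|---|
| unadjusted | 1.00 | 1.00 | 90.3% | 89.8% | 66 |
| 0.3 | 0.65 | 0.81 | 98.1% | 98.0% | 43 |
| 0.5 | 0.75 | 0.87 | 96.4% | 96.2% | 49 |
| 0.7 | 0.85 | 0.92 | 94.2% | 93.9% | 56 |
| 0.8 | 0.90 | 0.95 | 93.0% | 92.6% | 59 |

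At r = 0.3, 0.5 and 0.7 the gain equals 1/0.65, 1/0.75 and 1/0.85, that is 54%, 33% and 18% more patients. If change is uncorrelated with baseline the ratio is 1 and nothing is gained.

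**3. The same in terms of the interval.** The unadjusted 95% half-width is 1.960 × √(2/59) = 0.36 g. Multiplied by the residual SDs for r = 0.3, 0.5 and 0.7 it becomes 0.29, 0.31 and 0.33 g.

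**4. CHRONiGaN.** The ratio (1 + r)/2 does not depend on effect or SD, so the proportional gain is the same under the same assumptions. Power cannot be stated, because the protocol gives neither input.

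**5. Does leaving the test open threaten type I error?** Simulation with 4,000 trials per setting, 59 per arm and assumed r = 0.5, for normal and for lognormal proteinuria:

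- Choosing the test by a normality pretest: 4.6% to 5.0%.
- Taking the smaller of the two p-values, which the protocol does not propose: 5.9% (normal) and 6.5% (lognormal).

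The open choice is mainly a problem of matching the p-value to the estimate, not of error control.

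**The case against.** The strongest reply is that nothing here is invalid. Randomisation makes the unadjusted comparison unbiased, the trial is sized for it, and adjustment only adds power beyond the target. That stands, and it limits the point to efficiency and clarity.

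The gain also rests on an assumed correlation and on equal variances. That stands too. Nor does raw-scale ANCOVA win everywhere. In the lognormal simulation with an additive 0.6 g shift, power was 98% for Mann-Whitney, 93% for ANCOVA and 85% for the t-test. Even there, ANCOVA beat the other method that targets the mean difference the plan reports.

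The stratification argument is modest. With 132 patients over at least 30 sites there are about 4.4 per site (132/30) before splitting by age and sex, so little balance can be imposed and the conservatism is probably small.

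It can also be said that an analysis plan may add covariates. But the protocol has already given unadjusted tests for continuous comparisons and labelled the repeated-measures model secondary, so the protocol text itself needs changing.

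Some stronger readings are tempting but unsupported:

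- **Randomised patients without a final value are dropped and intention-to-treat is not met.** Sections 6.4 and 6.5 state an intention-to-treat analysis of all randomised patients, and no passage excludes those with missing values. Handling of missing values may sit in an analysis plan that is not shown.
- **The primary test is chosen after seeing the data.** The protocol ties a choice to the observed distribution explicitly only for mixed model versus GEE, a secondary analysis.
- **The 1.2 g mean fall contradicts entry at 0.5 g.** One is a planned mean with SD 1.0, the other an entry minimum; they can coexist.

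**Conclusion.** The point holds as a matter of precision and pre-specification. The protocol does not name one test for its primary endpoint, leaves out a baseline measured in everyone, omits the factors that stratify randomisation, and allows a p-value that does not belong to the reported mean difference.

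For ACiGaN, power would rise from about 90% to about 94% to 98% for an assumed correlation of 0.7 down to 0.3, given equal variances, the protocol's SD and difference, and 59 evaluable per arm. It would not rise at all if change were uncorrelated with baseline. A reader might infer that the 132-patient size is wrong or that the result would be biased; neither follows. The change is worthwhile because it costs almost nothing, not because the present test is unsound.

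**What to change.** In section 6.4, name one primary analysis for each trial before any outcome data are examined:

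- ANCOVA of 24-hour proteinuria at the primary time point, or the mixed model now listed as secondary with the treatment contrast at that time point.
- Adjustment for baseline proteinuria, age and sex, with centre as a random effect or pooled, given over 30 sites.
- The adjusted mean difference in g/24 h with its 95% CI and the p-value from the same model.
- The t-test, Mann-Whitney test and a log-scale analysis as sensitivity analyses.

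Keeping g/24 h for the primary result matters: a geometric mean ratio would change the quantity estimated, and the 0.6 g sizing would no longer describe it. The primary time point must also be settled, since section 6.4 uses 6 and 12 months while section 4.4 uses 4 and 8 months and 10 months; that is a separate matter.

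The cost is a change of wording. Proteinuria, age, sex and centre are already recorded, repeated proteinuria measurements are already scheduled, and the sample size can stay as it is.

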
Endpoints
	
Primary endpoint:
 
 • Between-arms difference in proteinuria reduction within 4 months and in non-responders within 8 months in ACiGaN study. • Between-arms difference in proteinuria reduction within 10 months in CHRONiGaN study. 
Secondary endpoints:
 
 • eGFR slope calculated as mean of individual slope obtained from individual linear regression of eGFR overtime (3 years); • eGFR decline > 40 % from the baseline value; • composite end point: GFR decline > 40%, ESKD (defined as long-term GFR ≤ 15 ml/min/1.73m² for more than three months or need for maintenance dialysis or kidney transplantation) or death due to kidney disease; • absolute difference between last GFR value and baseline GFR; • stable renal function defined as a decline in GFR ≤ 5 ml/min/1.73m² at the end of three years follow- up; • mean annual change in the slope of the reciprocal of serum creatinine concentration;

	
 time-averaged proteinuria (TA-P) calculated as the weighted mean of all post-randomisation measurement, with weights representing the time elapsed since the previous measurement; proteinuria slope, calculated as a mean of individual slope, obtained from individual linear regression of daily proteinuria overtime (3 years); complete remission of proteinuria defined as achievement of urinary protein level ≤ 0.2 g/day or a urinary protein-to-creatinine ratio ≤ 0.2 g/g; partial remission of proteinuria defined as achievement of a urinary protein reduction $\geq 50\%$ or greater compared with the baseline value.
Number of Sites	Over 30
Number of patients	
432 patients:
 
 132 patients (66 patients per group, including a 10% dropout rate, in the ACiGaN trial) 300 patients (150 patients per group, including a 10% dropout rate, in the CHRONiGaN trial)

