
Study Products
	
Methylprednisolone succinate and prednisone (Corticosteroids, CS) Dapagliflozin (Sodium-glucose cotransporter 2 inhibitor, SGLT2i)

Treatments
	
ACiGaN Study
 
IgAN Active renal lesions
 
Experimental arm: Corticosteroids + RASBs (4 months) → RASBs (4 months) → RASBs (28 months)
 
Control arm (KDIGO): RASBs (4 months) → RASBs + Corticosteroids (4 months) → RASBs (28 months)
 <hr/> 
CHRONiGaN Study
 
IgAN Chronic renal lesions Moderate renal lesions
 
Experimental arm: RASBs (4 months) → RASBs + Dapagliflozin (6 months) → RASBs + Dapa (26 months)
 
Control arm (KDIGO): Run-in → RASBs + Corticosteroids (6 months) → RASBs (26 months)
 
Patients will be randomized separately in each trial (allocation 1 to 1 ratio). Stratified randomization will be done by age and sex in renal centers.
 
ACiGaN trial
 
Experimental arm: Early corticosteroids therapy combined with RASBs followed by RASBs treatment.
 
Control arm (standard care): RASBs treatment followed by corticosteroids combined with RASBs and then only RASBs.
 
CHRONiGaN trial
 
Experimental arm: RASBs therapy followed by Dapagliflozin combined with RASBs.
 
Control arm (standard care): RASBs therapy followed by Corticosteroids combined with RASBs and then RASBs alone

Sample Size and Statistics
	
ACiGaN. Data from the literature have shown a difference in renal survival between corticosteroids and controls when the researchers assumed a difference of 50% in the primary end point (i.e., in the between-arms difference of delta 24 hour proteinuria from base-line to 6 months) as clinically relevant. Therefore, we assume that a mean delta proteinuria from base-line to 6 months in patients treated with RASBs alone (control arm) is 0.6 ± 1.0 g/24 hours (\pmSD) versus a mean delta proteinuria 1.2 ± 1.0 g/24 hours (\pmSD) from base-line to 6 months in patients treated with RASBs and corticosteroids (experimental arm). Based on these assumptions, we calculated a sample size of 132 patients (66 patients per group including a 10% dropout rate) for a power of 90%, a two-sided significance level of 0.05 and 3 years

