To our knowledge, this is the first study in which corticosteroids are administered immediately after the kidney biopsy in IgAN patients with active renal lesions. Based on the existing evidence from randomized clinical trials, the KDIGO guidelines suggest in those cases: RASBs for 3-6 months and then corticosteroids in presence of persistent proteinuria and $GFR >30$ ml/min/1.73 m². This therapeutic approach, although supported by evidence, may be a challenge based on empiric clinical knowledge supported also by findings of cohort studies. This demonstrates that after 3-6 months active renal lesions become chronic and consequently no association may be found between exposure to corticosteroids and clinical response for IgAN patients. In our randomized clinical study we compare the standard approach proposed by KDIGO guidelines (RASBs for 3-6 months followed by corticosteroids) vs a novel approach consisting of early corticosteroid therapy combined with RASBs from the beginning.

CHRONIgAN TRIAL

Patients with chronic (T1,2) or moderate renal lesions (M0,1; S0,1, E0, C0, T0) will be enrolled in a two-arm trial with 1:1 allocation ratio to compare Dapagliflozin combined with RASBs (experimental arm) versus corticosteroids combined with RASBs (control arm) after 4 run-in months of RASBs treatment. The enrolled patients will have proteinuria ≥ 0.5 g/day and GFR ≥ 30 ml/min/1.73 m².

Participants will receive study treatments by 4 weeks from the kidney biopsy.

Patients assigned to the experimental arm will receive RASBs therapy (4 run-in months) followed by Dapagliflozin (10 mg /day orally) combined with RASBs for a total of 32 consecutive months. Patients assigned to the control arm will receive RASBs therapy (4 run-in months) followed by oral corticosteroids therapy (prednisone) for six months (0.4 mg/kg body weight for 2 months and then gradual reduction of 5 mg/day for 4 months) and then RASBs alone for a total of 36 consecutive months.

This is a parallel group, two arm, superiority trial with 1:1 allocation ratio.

Rationale of the study design

We decided the combination Dapagliflozin and RASBs because recently, SGLT2is were administered in patients with type 2 diabetes and in other participants with CKD (some of them were affected by IgAN) (29-31). In these studies, the effect of SGLT2is was compared with a placebo.

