4.4 Outcome measures

The primary endpoint is the 24 h-proteinuria reduction between arms as suggested by Inker LA et al (44). It will be assessed after 4 and 8 months in the ACiGaN study and after 10 months in the CHRONiGaN trial.

The secondary end point is the GFR slope calculated as the mean of individual slope obtained from individual linear regression of eGFR overtime (3 years). Based on the International Consensus definition of clinical trial outcomes for kidney failure (23) we have also considered other secondary end points listed below.

Primary and secondary end points that will be evaluated in the two RCTs are listed below:

Primary endpoint:

- Between-arms difference in proteinuria reduction within 4 and 8 months in ACiGaN and within 10 months in CHRONiGaN study.

Secondary endpoints:

- eGFR slope calculated as mean of individual slope obtained from individual linear regression of eGFR overtime (3 years);
- eGFR decline > 40 % from the baseline value;
- composite end point: GFR decline > 40%, ESKD (defined as long-term GFR \leq 15 ml/min/1.73m² for more than three months or need for maintenance dialysis or kidney transplantation) or death due to kidney disease;
- absolute difference between last GFR value and baseline GFR;
- stable renal function defined as a decline in GFR \leq 5 ml/min/1.73m² at the end of three years follow-up;
- mean annual change in the slope of the reciprocal of serum creatinine concentration;
- time-averaged proteinuria (TA-P) calculated as the weighted mean of all post-randomization measurement, with weights representing the time elapsed since the previous measurement;
- proteinuria slope, calculated as a mean of individual slope, obtained from individual linear regression of daily proteinuria overtime (3 years);
- complete remission of proteinuria defined as achievement of urinary protein level \leq 0.2 g/day or a urinary protein-to-creatinine ratio \leq 0.2 g/g;
- partial remission of proteinuria defined as achievement of a urinary protein reduction \geq 50% or greater compared with baseline value.

The end points will be evaluated monthly in IgAN patients with active renal lesions in the first eight months after kidney biopsy and then every three months. In IgAN patients with chronic or moderate renal lesions the end points will be evaluated every three months in the first two years after the enrollment and then every six months.

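### CHRONiGaN's primary endpoint is set at 10 months, but Section 6.4 analyses it at 12 months, and the two dates compare the arms in different treatment states

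*Protocol*

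**What the plan says.** The protocol places the CHRONiGaN primary endpoint at month 10 in these places:

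- Synopsis, Endpoints: "Between-arms difference in proteinuria reduction within 10 months in CHRONiGaN study".
- Section 4.4, on the primary endpoint: "It will be assessed after 4 and 8 months in the ACiGaN study and after 10 months in the CHRONiGaN trial". The endpoint list in that section repeats the 10 months.
- Figure 2B: the primary-endpoint row has its first mark at t10 and is then marked at every later visit to t36.
- Section 6.5: the persistent population is defined by 10 months on the investigational drugs.

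Section 6.4, which states how the primary contrast is to be expressed, instead gives "the between-arms difference of delta 24h proteinuria from baseline to 12 months in the CHRONiGAN trial".

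The treatment timeline is in Section 3. Control patients receive "RASBs therapy (4 run-in months) followed by oral corticosteroids therapy (prednisone) for six months", then RASBs alone. Experimental patients have the same run-in, "followed by Dapagliflozin (10 mg /day orally) combined with RASBs for a total of 32 consecutive months".

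On visits, Section 4.4 says that in CHRONiGaN "the end points will be evaluated every three months in the first two years after the enrollment and then every six months". Figure 2B schedules daily proteinuria at t1, t4, t8, t10 and t12, among other visits.

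**The concern.** The primary time point is fixed twice, with different values, and nothing in the protocol reconciles them. The difference is more than two months on the calendar. Month 10 is when the control arm's steroid course ends, so moving to month 12 changes what is being compared.

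The trial is open label. If both dates stand, either could later be presented as the prespecified one once results are visible. A later SAP cannot settle this alone, because the protocol is not silent on the date. Whichever date a SAP chose, it would contradict one part of the protocol.

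**Working it through.** **1. Timeline, counted from allocation (t0, as in Figure 2B).** Inputs are from the synopsis treatment scheme and Section 3.

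- Control: 4 months RASBs + 6 months RASBs with prednisone + 26 months RASBs = 36 months.
- Experimental: 4 months RASBs + 32 months RASBs with dapagliflozin = 36 months.
- Both totals agree with the planned 36 months. Steroids end at 4 + 6 = month 10.

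**2. State of each arm at the two dates.**

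| | Month 10 | Month 12 |
|---|---|---|
| Control | 6 months of prednisone completed, at the end of its reduction | 12 − 10 = 2 months off steroids |
| Experimental | 10 − 4 = 6 months of dapagliflozin, continuing | 12 − 4 = 8 months of dapagliflozin, continuing |

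**3. Sensitivity to the anchor.** Section 3 describes the comparison as coming after the 4-month run-in. If months were counted from the end of the run-in, 10 months would be month 14 from allocation (14 − 10 = 4 months off steroids) and 12 months would be month 16 (6 months off). The anchor therefore has to be stated along with the date.

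**4. Visit dates.** Every three months gives 3, 6, 9, 12 and so on, which includes 12 but not 10. Figure 2B includes both.

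**5. Scale.** Section 6 gives CHRONiGaN 150 patients per group including 10% dropout, with no effect size, SD or power. There is no sample-size calculation to reproduce. Assumptions for illustration:

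- Evaluable per arm: 150 × 0.9 = 135.
- SD of change: 1.0 g/24 h, borrowed from the ACiGaN assumption, with a range of 0.8 to 1.2.

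Standard error = SD × √(2/135) = SD × 0.1217. The 95% half-width is 1.96 × SE:

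- SD 0.8: 0.19 g
- SD 1.0: 0.24 g
- SD 1.2: 0.29 g

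Now suppose the arms are truly equal at month 10, and by month 12 the control mean rises by d while the experimental arm is unchanged. The chance of a significant result is about Φ(d/SE − 1.96):

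| True rise d (g/24 h) | SD 1.0 | SD 0.8 to 1.2 |
|---|---|---|
| 0.1 | 13% | 10 to 18% |
| 0.2 | 38% | 28 to 54% |
| 0.3 | 69% | 54 to 87% |

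For d = 0.24 and SD 1.0, 0.24/0.1217 = 1.97, so the chance is Φ(0.01), about 50%.

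**The case against.** Nobody can fairly deny that 10 and 12 both appear. The case on the other side is about consequences, and much of it stands.

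- **Bias towards dapagliflozin.** A reader might infer that a 12-month analysis is tilted in favour of the experimental arm. The protocol has no data on proteinuria after prednisone stops, and a lasting steroid effect would leave little or no shift. Month 10 is not a full-dose comparison either, since prednisone is reduced over the last four of its six months. Unequal treatment duration is part of the design, so a 12-month intention-to-treat comparison of the two strategies is a legitimate question. It is a different question from the one in the endpoint definition.
- **Lost month-10 data.** A reader might infer from the three-monthly sentence that sites would not collect the 10-month value. That is unlikely. The same section says the endpoint is assessed after 10 months, and Figure 2B already schedules proteinuria at t10. What remains is an inconsistency of wording.
- **Figure 2B as proof of month 10.** The primary-endpoint row starts at t10 but continues through t12 to t36. It supports 10 as the first date and does not exclude 12.
- **A 0.24 g rebound as decisive.** That figure equals the CI half-width under the assumed SD. A true rebound of that size gives significance only about half the time, and the SD comes from a different population.

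None of these points removes the contradiction.

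**Conclusion.** The point holds as an internal contradiction about the primary time point: 10 months in the synopsis and Section 4.4, with Figure 2B and Section 6.5 consistent with that, against 12 months in Section 6.4. The two dates are different contrasts, because one arm's add-on therapy ends at month 10 and the other's does not. That conclusion rests on counting months from allocation.

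The documents do not establish that the 12-month version is biased, in which direction, or by how much. The figure of 0.24 g/24 h (0.19 to 0.29) gives scale only, and it depends on the borrowed SD and on 135 evaluable patients per arm. The practical risk is that an open-label trial with two stated primary dates leaves the choice open until data are visible. It should be closed before any outcome data are seen.

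**What to change.** Before outcome data are seen:

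1. In Section 6.4, replace 12 months with 10 months for the CHRONiGaN primary contrast. This matches the endpoint definition and the existing t10 visit.
2. State the anchor: baseline is the pre-allocation value and months count from allocation, or name another anchor explicitly.
3. Keep 12 months as a secondary time point, labelled as falling after the end of the control arm's steroid course.
4. Reconcile the three-monthly sentence in Section 4.4 with Figure 2B, which already has proteinuria at t4, t10 and t12.
5. Reconcile the ACiGaN half of the same Section 6.4 sentence, which uses 6 months where the synopsis and Section 4.4 use 4 and 8 months.

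The cost is a protocol amendment of wording, submitted to the ethics committees if it counts as substantive under Section 8.2. No visits are added.
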